All 3 pilot test sites will be followed for up to 6 months. To implement the interventions and assess for issues in the implementation process in order to further refine the intervention plan, information will be collected regarding the process of ADT ordering at each site, including who is involved, through conversations with the Site Champion (who is also a project consultant) or their designee. Additionally, information regarding implementation status as well as any changes in site processes around prescribing ADT will be discussed at regular team meetings with the project consultants (including Site Champions). For both the pilot and implementation trial, outcomes will be collected from VA CDW/Cancer Registry/Vital Status/CMS records and CPRS/Capri/JLV/WebVRAM for all clinic visits documented as providing low-value ADT at baseline, 3 and 6 months. An organizational survey will be developed and refined throughout the pilot. For the pilot implementation trial, an anonymous clinic assessment survey will be administered to Site Champions at baseline and an ADT provider assessment will be administered to participating site providers at baseline and 1-month post-intervention through VA Qualtrics (Appendix VI).

Outcomes Analyses

Primary analyses: Comparing the effectiveness of two de-implementation strategies, **Or** vs. **Sc**, on continued low-value ADT use after six months. Our primary outcome is stopping ADT injections, which will likely be evaluated through a combination of chart reviews and informatics data generated through the ordering process. We will also explore the feasibility and impact of six-month outcomes during pilot testing to increase study efficiency and timeliness.

Secondary outcomes: RE-AIM implementation outcomes, changes from baseline measures, total ADT injections per arm at 6 months post implementation. (Table 4). We will examine moderators of strategy effectiveness (e.g., fidelity) and causal mechanisms underlying the strategies through content analysis from study team and pilot site meeting documents and discussion and based on our organizational assessment.

Table 4. Implementation Outcomes (based on the RE-AIM framework)

Domain	Order entry	Script
Reach	$(1 - \# \text{ ADT providers opt out}) / (\text{total ADT providers})$	$(1 - \# \text{ ADT provider opt out}) / (\text{total ADT providers})$

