Effectiveness *** (primary implementation outcome, and primary outcome of trial)	Low value ADT (LVADT) prescription order decrease $(\text{LVADT candidate expected orders} - \text{LVADT not ordered}) / (\text{LVADT got order} + \text{LVADT stopped order})$	
Adoption (provider level)	At least 1 order fired and signed (provider level)	At least 1 script signed (provider level)
Penetration Adoption (order level)	$(\# \text{ times order entry justified}) / (\# \text{ times order went through anyway})$	$\# \text{ scripts signed} / (\text{LVADT got order} + \text{LVADT stopped order})$
Implementation	Did implementation vary? 
- Differential adoption/penetration in medical oncology vs radiation oncology vs urology- Measure adoption/penetration at different time points (e.g., 3/6 months)- Number of sites that withdraw from participation (e.g., 3/6 month withdrawal rates)	
Fidelity	
- Were the justifications appropriate? (i.e., was something entered, or was no reasoning put in (enter n/a, etc))	
- Was the script edited? (i.e., not just signed)
Maintenance (site/setting level)	Proportion of sites that would elect to continue intervention, if available	

TIMELINE

R37 Funding: 1/1/2022 – 12/31/2023

PILOT SITE SELECTION

- The **Or** and **Sc** interventions will be piloted at the study PI and consultants' sites as follows:

Site	Site Champions	Intervention
VA Ann Arbor Healthcare System	[name] (co-PI)	Or & Sc
VA Greater Los Angeles Healthcare System	[name]	Or
VA New York Harbor Healthcare System	[name]	Or

PILOT SITE IMPLEMENTATION OVERVIEW

- Drs. [name], [name], and [name] are all consultants who have agreed to serve as Site Champions for the pilot work.
 - Study consultants do not have access to identifiable data or the study folder and are not "engaged" in study activities.
- Pilot sites will not be randomized.
- The ADT Order Check Attestation Intervention (**Or**) will be implemented at all sites, as this intervention requires engagement with other services, such as CAC, pharmacy, etc., and its procedures are most in need of refinement.
- The ADT Provider Script Intervention (**Sc**) will be implemented at Ann Arbor.
- The official start date for the pilot begins when we have started adding HF's and/or assigning progress notes. Pilot sites will be followed for up to 6 months.
- Facility Notifications & Approvals

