- Once the CROC has been switched to live mode, study staff will place a "Living Well ADT" health factor in the EMR of patients whose clinic visits study staff have confirmed to be targets for ADT de-implementation. We will enter health factors as we identify eligible patients. This health factor combined with a low PSA level (most recent PSA < 2ng/mL) will trigger the ADT Order Check Attestation Intervention (**Or**) when the provider places an order for ADT (Lupron, Eligard, Viadur, Goserilin, and Zolodex).
- Providers may override the CROC by entering a number from the order check text that corresponds to the reason they are overriding the order check. Providers are also able to enter text if a numbered reason is not listed.
- If providers opt-out after the health factor was placed for one of their patients, study staff will remove the health factor in CPRS. For a provider who opts-out, the Study Data Manager will run a query in our Access tracking database to pull a list of his/her patients. The Study Team will not place a health factor in the EMR of patients whose provider has opted out.
- Study staff will do periodic quality control checks to ensure the intervention is working as expected and work with the site CAC's to make adjustments as necessary.
- Appropriate use of the indication will be tracked for fidelity. We will track comments entered by providers to override order checks. The Study Data Manager will periodically pull comments from order checks (there are data tables for order checks that contain text for open field that are stored in CDW).
 - Using a combination of progress notes and other CPRS data, study staff will check to determine whether the patient received the injection.
- Deimplementing Or – study staff will remove HFs for intervention patients. We'll ask site to remove study HF from their CPRS.

CPRS INSTRUCTIONS FOR OR INTERVENTION

OPENING CPRS

- Go to "VA Shortcuts" (star icon on desktop)
- Select "CPRS _Launcher" (rocket icon)
- Select: VISN 03 or VISN 22
- Select site: Ex - Manhattan, NY
- Launch CPRS button

PLACING A HEALTH FACTOR

While in a patient record in CPRS:

- Click on the "Notes" tab (bottom of screen)

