- Study staff will enter a CPRS progress note approximately one business day prior to a target low-value ADT clinic visit. Notes will not be assigned for ADT injection-only visits. The note includes talking points for the provider to help with a discussion with the Veteran.
 - The note can be edited and signed by the provider, giving a quick and simple way to document the discussion. The progress note will prompt providers to indicate whether patient prefers to continue or discontinue ADT.
- The progress note will include links to the clinic handout which will be posted on CCMR's external website (outside VA firewall).
- Providers may modify, ignore, or delete the progress note.
- Appropriate use of the indication will be tracked for fidelity. We will track how many notes are placed. We will also be able to run a report of all signed and unsigned progress notes.
- At the end of the intervention period, Ann Arbor CAC's will delete/remove all unsigned progress notes. Unsigned notes will need to be reassigned at the end of the study. [name], or another AAVA CAC will run a report of unsigned notes by our note title for Ann Arbor. The CAC will change the note author back to a member of the study team, which we can then remove from CPRS. We will ask the Data Manager to reassign the note in CDW for other sites or ask the site CAC if necessary.
 - If providers delete an unsigned note, it's unlikely to appear in a TIU progress note report.

CLINIC HANDOUT

- The clinic handout will be tailored to each individual facility, e.g., with site name (Appendix V).
- Prior to each site's scheduled IES, study staff will provide clinic handouts to the clinic point person identified by the Site Champion (the clinic point person may also be the Site Champion). We may use one or more of the following approaches:
 - By mail: hardcopies of the handout will be mailed to the clinic point person (as requested). Each clinic will receive 50 copies of the handout.
 - By email: copies of the handout will be emailed to clinic point person (this may happen when we send Site Champions the email templates or in a separate email). Each clinic will be instructed to print 50 copies of the handout.
 - By website: a copy of the handout will be accessible on CCMR's website (outside the VA firewall). A link to the website will be included in the progress note.

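### Table 4 credits Or adoption only when a flagged ADT order is signed, so a provider who cancels every flagged order is a non-adopter, and adoption and penetration are not comparable between arms

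*Protocol*

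**What the plan says.** The definitions are in the protocol, Outcomes Analyses, Table 4.

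- Adoption, Or: "At least 1 order fired and signed (provider level".
- Adoption, Sc: "At least 1 script signed (provider level".
- Penetration (order level), Or: the number of justified order entries divided by the number of orders that proceeded despite the check.
- Penetration (order level), Sc: the number of scripts signed divided by low-value orders placed plus low-value orders stopped.

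Section C2.1.2 lets the Or provider either proceed with a flagged order or cancel it, and the order-check screenshot carries an accept button and a cancel button. The Study Overview gives the goal of both strategies as less low-value ADT, and Outcomes Analyses gives the primary outcome as stopping ADT injections.

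Table 4 also has a fidelity row. For Or it reads "Were the justifications appropriate? (i.e., was something entered, or was no reasoning put in (enter n/a, etc"; for Sc it reads "Was the script edited? (i.e., not just signed".

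**The concern.** On its plain wording, the Or adoption rule needs two events: the check fires, and the ADT order is then signed. A cancelled order is never signed. The response that the check is meant to prompt therefore earns no adoption credit, and going ahead despite the check does. The Sc rule is neutral: a signed script counts whether ADT continues or stops.

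The penetration row repeats the asymmetry. Stopped orders are left out of the Or denominator and included in the Sc denominator.

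At stake is the between-arm reading of two RE-AIM implementation outcomes. A difference in adoption or penetration could come from the definitions rather than from how providers took up each tool. Within Or, a site where the check stopped more orders could show lower adoption.

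**Working it through.** The protocol gives no figure on this point to reproduce, so the check applies the Table 4 rules to each possible response and then illustrates the size.

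**Step 1. Classify the responses.**

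| Arm | Provider's behaviour | Low-value ADT | Adopter under Table 4? |
|---|---|---|---|
| Or | Cancels every flagged order | Stopped | No |
| Or | Cancels all but one, overrides one | Mostly stopped | Yes |
| Or | Overrides every check | Continues | Yes |
| Sc | Signs script, ADT stopped | Stopped | Yes |
| Sc | Signs script, ADT continued | Continues | Yes |

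Only the first row is misclassified, so the effect is confined to providers who cancel all their flagged orders.

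**Step 2. Size of the adoption effect.** Let k be the number of flagged orders for a provider and c the probability of cancelling each. Both are assumed, and cancellations are taken as independent.

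P(counted as adopter) = P(at least one of k orders is signed) = 1 − c^k

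The Chart Reviews section gives injection intervals of 1, 3 or 6 months. At one order per injection, that is 6, 2 or 1 orders per patient in six months; k = 10 stands for a provider with several patients.

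| k | c = 0 | c = 0.2 | c = 0.5 | c = 0.8 | c = 1 |
|---|---|---|---|---|---|
| 1 | 1.00 | 0.80 | 0.50 | 0.20 | 0 |
| 2 | 1.00 | 0.96 | 0.75 | 0.36 | 0 |
| 6 | 1.00 | 1.00 | 0.98 | 0.74 | 0 |
| 10 | 1.00 | 1.00 | 1.00 | 0.89 | 0 |

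For example, at c = 0.8 and k = 2, 1 − 0.8² = 1 − 0.64 = 0.36. Measured Or adoption falls as cancellation rises. The fall is large for providers with few flagged orders and small for those with many, unless nearly all orders are cancelled.

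**Step 3. Penetration.** Take 20 fired checks, s of them stopped, and every override justified.

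- Or as written: (20 − s)/(20 − s) = 1.0 at s = 0, 10 or 16, and 0/0 at s = 20.
- Or with the Sc-type denominator but no credit for cancelling: (20 − s)/20 = 1.0, 0.5, 0.2 and 0 at s = 0, 10, 16 and 20.
- Or with that denominator and cancelled orders counted as a response: (20 − s + s)/20 = 1.0 at every s.

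Matching the denominator alone would carry the adoption fault into this row, so the numerator has to credit cancellations too. The corrected measure still discriminates: with s = 10 and only 5 of the 10 overrides justified, it is (10 + 5)/20 = 0.75.

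**The case against.** **Signed may mean only that the check was acknowledged.** That is possible, but the text does not say so. The penetration row beside it also leaves stopped orders out for Or, which points the other way.

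**Or is an attestation tool, so counting documented overrides is a coherent idea of adoption.** This stands in part. It is incomplete because it gives no credit for cancelling.

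**One override makes a provider an adopter, so with many flagged orders little changes.** This stands, as Step 2 shows.

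**A reader might infer that the definition tilts the comparison toward Sc.** The documents do not support that. Sc notes can be ignored or deleted and are not assigned for injection-only visits, so Sc adoption may be the lower of the two. Non-comparability is shown; its direction is not.

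**A reader might also infer that the fidelity row penalises intended use and would give a moderator result with the wrong sign.** The documents do not support this either. The Progress Note section says "The note can be edited and signed by the provider, giving a quick and simple way to document the discussion", and the note prompts for a continue or discontinue choice, so complete use would normally involve an edit. For Or, "Providers may override the CROC by entering a number from the order check text" means that a listed code passes the test of "was something entered, or was no reasoning put in". That rule is lenient and does not penalise the intended response. The protocol does say "We will examine moderators of strategy effectiveness (e.g., fidelity" among its secondary analyses, but by content analysis of meeting material and the organizational assessment. It states no model in which a sign could reverse. What remains is a labelling point: whether something was entered measures completion rather than appropriateness.

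**The measures are to be refined during the pilot.** Study Design, Pilot Data Collection and Trial Data Collection all say this. It softens the point. But the current text gives no replacement definition, although it already carries note-assignment instructions for trial sites.

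**Conclusion.** The point holds for adoption and penetration. As written, an Or provider who cancels every flagged order is a non-adopter, an Sc provider is credited whatever the ADT decision, and the two penetration ratios rest on different denominators. Neither outcome can be compared between arms.

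The size depends on two quantities the protocol does not give: the cancellation probability and the number of flagged orders per provider. Under independent cancellation, the shortfall in measured adoption among Or providers with at least one fired check is c^k. At c = 0.8 that is 0.80 with one order and 0.11 with ten. The claim does not extend to a known direction of bias between arms or to the fidelity row.

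Both are secondary implementation outcomes. The primary outcome, stopping ADT injections, uses neither row. The change is still worth making, because the fault lies in a stated rule and is easy to correct.

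**What to change.** Reword Table 4 as follows.

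- **Adoption, Or:** at least one fired check acted on, either by cancelling the order or by overriding with a reason, among providers with at least one fired check. Report cancelled and overridden separately. Because the screen asks for one response or the other, the combined rate may sit near its ceiling, and the split will carry most of the information.
- **Adoption, Sc:** at least one note signed, among providers assigned at least one note.
- **Penetration, both arms:** use low-value orders placed plus orders stopped as the denominator. In Or, count a cancelled flagged order as a response in the numerator, alongside justified overrides.
- **Fidelity, Or (optional):** label the entry of any reason as completion and not as appropriateness.

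The cost is small but goes beyond rewording. The Or section describes pulling override comments and checking whether the injection was given. The new rule also needs each cancelled flagged order to be attributed to a provider, from ordering data or chart review. Table 4 already calls for a count of stopped orders, but that count alone does not show that a check fired or who cancelled.

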- We will collect data using CDW/Cancer Registry/Vital Status/CMS data from October 1, 1999 to June 30, 2024
- Study Data Manager will identify the low-value ADT cohort using 2020 - 2022 VA CDW/Central Cancer Registry/Vital Status/CMS data.
 - Real SSNs will be necessary in order to link data across databases and to conduct chart reviews.
- Target clinic visits appropriate for low-value ADT de-implementation will be identified using CDW/Cancer Registry/Vital Status/CMS data based on patient diagnosis, PC treatment, and treatment dates.
- We developed real-time 'smart' criteria to support streamlined implementation including:
 1. Injectable ADT order within 14 months of the current date (e.g., leuprolide J9217)
 2. Prostate cancer diagnosis (ICD-9 185, ICD-10 C61)
 3. Low and non-rising PSA levels consistent with localized disease or treated non-metastatic biochemically-recurrent prostate cancer (<2 ng/mL)
- Clinic visits identified as appropriate for ADT de-implementation will include all those with patients undergoing ADT monotherapy as well as those with non-metastatic prostate cancer after definitive treatment, and those receiving continuous ADT for biochemical recurrence.
 - **ADT monotherapy/primary ADT is defined by:**
 1. Never had evidence of metastatic disease (including bones and lymph nodes)
 2. No treatment with castration-resistant prostate cancer (CRPC) medications (e.g., abiraterone, enzalutamide)
 3. No definitive treatment with radiation (+/- adjuvant ADT), RP, or cryotherapy, and has no immediate plan for definitive treatment
 4. Receiving ongoing ADT at the VA
 5. Current PSA ≤ 2 and not rapidly rising (no PSADT < 10 months)
 - **Biochemical recurrence is defined by:**
 1. Never had evidence of metastatic disease (including bones and lymph nodes)
 2. No treatment with CRPC medications (e.g., abiraterone, enzalutamide) in the last two years
 3. Has completed definitive treatment with radiation (+/- adjuvant ADT), RP, or cryotherapy
 - The course of adjuvant ADT not within 3 years of definitive treatment
 4. Rise in PSA level after definitive treatment
 - 2 ng/mL over nadir for those with history of radiation treatment

- nadir = lowest PSA after treatment
 - >0.2 ng/mL for those with radical prostatectomy (RP)
- 5. Receiving ongoing ADT at the VA for biochemically recurrent prostate cancer
- 6. Not on adjuvant ADT with salvage radiation

- **nmPCa after local/definitive treatment defined by:**

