 1. Never had evidence of metastatic disease (including bones and lymph nodes)
 2. No treatment with CRPC medications (e.g., abiraterone, enzalutamide) in the last two years
 3. Has completed definitive treatment with radiation (+/- adjuvant ADT), RP, or cryotherapy
 4. Receiving ongoing ADT at the VA
 5. No rise in PSA level after definitive treatment
 - Current PSA ≤2 and not rapidly rising (no PSADT <10 months)

- Throughout the pilot, the data manager will complete data pulls at different time intervals (e.g., weekly, bi-weekly, monthly, etc.) to determine how often the data may need to be refreshed during the RCT. Data such as patient appointment cancellations, changes in PSA scores, new drug names, variations of appointments/treatments, etc. are important to keep updated as they can impact patient eligibility.

MPCA NATURAL LANGUAGE PROCESSING (NLP) TOOL USE IN VINCI

- We will use a validated NLP tool developed by the VA Salt Lake City Healthcare System Prostate Core to identify Veterans with metastatic prostate cancer (mPCa) in real time. This will enable us to further refine our cohort by excluding all mPCa patients.
 - The Prostate Core has provided a data dictionary for definitions of the variables.
 - We will inform the Prostate Core if any of our definitions are different (e.g., prostate cancer, mPCa, etc.).
 - In the event we find mPCa patients after we complete chart reviews, we will inform the Prostate Core team.
 - Study staff will view the NLP data output in a VINCI worksheet.

- The PCa Data Core table/list is updated monthly by VINCI (we should receive email notifications from VINCI when the list has been updated).

CHART REVIEWS

- Study staff will also **conduct chart reviews using CPRS/Capri/JLV/WebVRAM to confirm target ADT orders and clinic visits.**
 - Study staff will apply for local CPRS access at participating sites through WebVRAM, though Capri/JLV may also be used to conduct chart reviews

- As the ADT injections occur serially at 1, 3, or 6 month intervals, an individual provider could have multiple opportunities to be exposed to the intervention during the 6-month study period.

- Low-value ADT injections must have occurred within 14 months prior to data pull.

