- If requested by sites, the study will provide supplies to sites to display the clinic handouts. Study staff will check in to ensure handouts were received and are being displayed and/or made accessible to providers and to address any issues that come up.
- It is up to the discretion of the provider whether/how to incorporate the handout into the clinic visit discussion.

CPRS INSTRUCTIONS FOR Sc INTERVENTION

ASSIGNING A PROGRESS NOTE

1. Open TWO files:
 - a. CPRS
 - b. *Database
 - i. Note: Starting 8/10, [name] will assign progress notes for Columbia and Phoenix patients.
 - ii. Note: Starting 8/14, [name] will update the appointment list for eligible patients each week (on Mondays). The database will list dates of upcoming appointments in chronological order.
2. While in a patient record in CPRS:
 - a. Confirm patient name and SSN match what's in the database (you're just confirming that you're looking at the correct person in CPRS).
 - b. In CPRS, go to "Appointments" in the "Cover Sheet" to confirm that the appointment listed in the database matches what's listed in CPRS.
 - i. If the date and/or name of an upcoming appointment in CPRS is different than what is in the database, update the "Visit datetime" and "Clinic" name in the database.
- c. In CPRS, confirm the MOST RECENT PSA has not increased beyond 2ng/ml.
 - i. **IF** the patient has a PSA <2ng/ml, skip to Step 2d.
 - ii. **IF** the patient has a PSA >2ng/ml, go back to the database, open the form for the patient, click "View/Edit Chart Reviews" and edit the Patient Chart Review page:
 - 1) HF/Note Comments – add reason for not assigning progress note (i.e., why patient is ineligible) – comment should read as: "Prior to assigning note, it was confirmed the patient's most recent PSA on [DATE] was [PSA value]."
 - 2) Not Elig. At Visit box – check this box
 - 3) Exclusions – select "Yes" next to "Current PSA >2 or rapidly rising"
 - 4) Inclusions – mark all three inclusions "No"
 - 5) Notes – add reason for not assigning progress note (yes, you will repeat step 2.c.i.1) – comment should read as: "Prior to assigning note, it was confirmed the patient's most recent PSA on [DATE] was [PSA value]."
 - 6) Outcomes – mark "Not Eligible"
 - 7) Click "Save"
 - iii. Note: If the patient is ineligible for another reason (i.e., patient is deceased, provider opted out, etc.) follow steps 1)-7) to update this page. The details should be relevant to the specific situation.

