- d. In CPRS, confirm all other eligibility criteria. The patient must NOT meet any of the exclusion criteria prior to assigning a note.
- e. In CPRS, click on the "Notes" tab (bottom of screen).
- f. In CPRS, click on the "New Note" tab. *Location for Current Activities* dialog box will open.
- g. In CPRS, click on the "New Visit" tab (far right over tabs).
 - i. [PILOT] For Ann Arbor, enter "AA GM-LETTER-X" to attach the note
 - ii. [RCT] Enter the following to attach the note:
 - 1) Columbia – **WJB RESEARCH NOTES**
 - 2) Phoenix – **ADMINISTRATIVE CONTACT**

Version 6, 10/04/2023

Page 38 of 88

- h. Time of visit should be set to "Now" (do **NOT** check the "Historical Visit" button).
- i. Click "OK."
- j. ****In Progress Note Properties box, enter "ADVISORY-ADT FOR LOCALIZED/NON-METASTATIC PROSTATE CANCER".** Once you see the note title in the menu, click to highlight it, and then click "OK."
- k. *Reminder Dialog Template: Advisory - ADT for Localized/Non-Metastatic Prostate Cancer* box will open. Click "Finish."
- l. *Primary Encounter Provider* box may open. Enter the name of the provider. Once you see the provider's name in the menu, click to highlight it, and then click "OK."
- m. Tailor the note for each patient:
 - i. Delete one of the options in the first sentence "based on multidisciplinary review..." prior to assigning the note (primary ADT or BCR). Refer to the database to see the patient's eligibility.
- n. In the event you need to manually enter PSA lab values and ADT injection information, please include data for the **three most recent PSA labs and ADT injections within the last year.**
 - i. The best place to find this information is in the progress notes for an ADT injection appointment (they *may* include "Uro" or "Onc" in the title – do not assume information about an ADT injection is not available just because a note doesn't include "Uro" or "Onc" in the title). You can also find information about ADT injections in the progress notes and in the Meds tab.

UROLOGY CLINIC NOTE, WJB SURG GU PROV 2 CL MD, ← ADT discussion
 UROLOGY INJECTIONS NOTE, WJB SURG GU NURSING, ← ADT injection only appointment

- ii. If the patient doesn't have three ADT injections in the last year, just add the two most recent injections.
- iii. Refer to the progress note template to see what information should be included and how the section should be formatted.

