Exclusions 
 
 Provider Opted Out	Yes	No	
 
 Deceased	Yes	No	
 
 mPC-including local nodes	Yes	Unclear	No	
 
 VA ADT injections ongoing	No	IADT	CC (decisions made by community care)	Unclear	Yes	
 
 Current adjuvant ADT	Yes, having/had XRT	Yes, plan for XRT	Unclear	No	
 
 CRPC	Yes	No	
 
 Current PSA > 2 or rapidly rising	Yes	No	
 
 Other	Other (add comment on note section below)	Other Specify	
 
							Provider Opted Out	Yes	No	Deceased	Yes	No	mPC-including local nodes	Yes	Unclear	No	VA ADT injections ongoing	No	IADT	CC (decisions made by community care)	Unclear	Yes	Current adjuvant ADT	Yes, having/had XRT	Yes, plan for XRT	Unclear	No	CRPC	Yes	No	Current PSA > 2 or rapidly rising	Yes	No	Other	Other (add comment on note section below)			Other Specify
Provider Opted Out	Yes	No																																				
Deceased	Yes	No																																				
mPC-including local nodes	Yes	Unclear	No																																			
VA ADT injections ongoing	No	IADT	CC (decisions made by community care)	Unclear	Yes																																	
Current adjuvant ADT	Yes, having/had XRT	Yes, plan for XRT	Unclear	No																																		
CRPC	Yes	No																																				
Current PSA > 2 or rapidly rising	Yes	No																																				
Other	Other (add comment on note section below)			Other Specify																																		
Inclusions 
 
 Definitive Tx	Any	Unclear	No	
 
 ADT for BRPC	Yes	No	
 
 No PSA recurrence and >3yrs adj/adj ADT	Yes	No	
 
							Definitive Tx	Any	Unclear	No	ADT for BRPC	Yes	No	No PSA recurrence and >3yrs adj/adj ADT	Yes	No																						
Definitive Tx	Any	Unclear	No																																			
ADT for BRPC	Yes	No																																				
No PSA recurrence and >3yrs adj/adj ADT	Yes	No																																				
Next ADT Visit	Notes:																																					

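### Men on ADT after definitive treatment without PSA recurrence are a target group, but the Sc note has no correct indication for them, and their written definition lacks the chart-review form's adjuvant-ADT limits

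*Protocol*

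**What the plan says.** Under Identifying Low-Value ADT in Pilot, the protocol names three kinds of patient whose visits are targets: men on ADT monotherapy, "those with non-metastatic prostate cancer after definitive treatment", and men on continuous ADT for biochemical recurrence. The middle group (nmPCa after local/definitive treatment) has a five-item definition: no metastases ever; no drugs for castration-resistant disease in the last two years; "Has completed definitive treatment with radiation (+/- adjuvant ADT), RP, or cryotherapy"; current ADT at the VA; and no PSA rise since treatment, with PSA at most 2 and not rising fast.

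The Patient Chart Review Page in the study database treats this group as eligible under the inclusion "No PSA recurrence and >3yrs adj/adj ADT" and carries the exclusion "Current adjuvant ADT". The Sc instructions confirm that the form has three inclusions: for a man found ineligible, staff are told to "mark all three inclusions" as No.

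The Sc progress note opens with a sentence giving the indication, introduced as the finding of multidisciplinary review. It has two bracketed alternatives, primary therapy or treatment of biochemical recurrence. Step 2m of Assigning a Progress Note tells staff to delete one of them "prior to assigning the note (primary ADT or BCR", and the bracket lists nothing further. The Or alert (Screenshot of CPRS Order Check) says only that PSA is below 2 and that metastatic disease is not apparent.

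**The concern.** The note is the Sc intervention. A third-group man is eligible, yet staff who follow the instructions have no true sentence to leave in his note. The provider then receives a wrong indication under the authority of a multidisciplinary review, followed by guideline advice for that clinical scenario.

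This also touches a measured outcome. Table 4 judges Sc fidelity by whether the script was edited and not merely signed. A provider who only corrects the indication would count as having edited it, unless the content of the edits is read.

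The second issue is which rule defines the group. If the written definition is wider than the form, anyone who counts or selects men from the definition alone can include men whose adjuvant ADT is planned and justified. Trial Data Collection asks whether control-site patients would have been eligible but does not say by which rule.

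**Working it through.** There is no sample size, power or error rate to recompute. The check sets the texts side by side.

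**1. Do the two note labels fit the third group?**

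| Note label | What the protocol requires for that label | What the third group requires | Compatible? |
|---|---|---|---|
| Primary ADT | No definitive treatment (monotherapy definition, item 3) | Definitive treatment completed (item 3) | No |
| Biochemical recurrence | PSA rise after definitive treatment (recurrence definition, item 4) | No PSA rise after definitive treatment (item 5) | No |

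Three target groups minus two labels leaves 3 − 2 = 1 group without a valid label. Step 2m sends staff to the database for the man's eligibility, but the database holds three inclusions and the note only two choices.

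**2. Was this repaired later?** The template update of 7/27/2023 is recorded as changing only the ADT injections section, and its sample text again carries the recurrence label. The note-assignment instructions, on pages marked Version 6 of 10/04/2023, still list two options. They name trial sites, so they apply to the trial as well as the pilot.

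**3. Does the same fault exist in the Or arm?** No. The alert's statement about PSA and metastases is true of a third-group man.

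**4. Do the written definition and the form agree?** Take a man who has finished radiation, is in a planned adjuvant course given at the VA, has a suppressed PSA, and has had neither metastases nor drugs for castration-resistant disease.

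- Written definition: he meets all five items. None excludes a current adjuvant course or sets a duration.
- Form: he fails, because "Current adjuvant ADT" is an exclusion. The inclusion for this group also asks for more than 3 years. Its abbreviation is read here as adjuvant ADT, and the form does not say when the 3 years start.

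The parenthesis on adjuvant ADT in "Has completed definitive treatment with radiation (+/- adjuvant ADT), RP, or cryotherapy" might be thought to require that the adjuvant course is over. The recurrence definition uses the same words and still adds "The course of adjuvant ADT not within 3 years of definitive treatment", so the protocol does not treat the parenthesis as a sufficient limit. Even if it did, the 3-year criterion would still be missing from the third-group definition.

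**The case against.** On the label, the note is hedged (the patient appears to be on ADT for the stated reason), its title fits any non-metastatic patient, and the talking points do not change with the indication. The provider may modify, ignore or delete it. All of this stands and limits the harm. It does not make the sentence true when it is sent, and no step in the instructions corrects it.

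On the definition, the case against is stronger. The data pull yields potentially eligible men, chart review confirms them, and the form's exclusions must be cleared before a note is assigned. The form's outcome options cover both the health factor (Or) and the note (Sc), so one form already serves both arms. Under Chart Reviews, visits with proper justification for ADT are dropped. A broad pull followed by a narrower screen is normal practice. The protocol also mentions a chart review guide that is not shown and may state the rule for control sites. This is why the definition is the secondary point.

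A reader might infer more from the adjuvant-ADT texts than they support:

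- The recurrence list also has "Not on adjuvant ADT with salvage radiation". Salvage radiation presupposes recurrence, so its absence from a no-recurrence group is not an omission.
- The form's 3-year item might be converted into a span of months over which the two rules disagree. The label is abbreviated and its starting point is not given, so no such span can be derived.
- Section B1 mentions long adjuvant courses as further low-value use. It presents them as a later opportunity and not as a target of this trial, so leaving those men out does not conflict with it.

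**Conclusion.** The label gap holds as written: one of three target groups has no correct option in the Sc note, and any note sent for such a man misstates why he is on ADT. It is a defect in the intervention text of one arm and should be corrected. The definition gap is real but smaller. The third-group definition is literally wider than the form, while the form and the review steps should keep most men on justified adjuvant ADT out of both arms.

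A reader might infer that the Or versus Sc comparison is biased, or that many men are wrongly selected. The protocol does not support either. It gives no count of third-group men or of men on adjuvant ADT, and it does not show that the wrong label changes prescribing. The effect on the primary outcome is probably small and is not quantified.

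The conclusion rests on two assumptions: that the form's abbreviated inclusion refers to adjuvant ADT, and that staff follow the note instructions as written.

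**What to change.** 1. Add a third bracketed option to the Sc note and to step 2m, for ADT continuing after definitive treatment without PSA recurrence.
2. Add the form's two criteria to the nmPCa definition: not on a current adjuvant course, and more than 3 years of adjuvant ADT. Spell out the abbreviation and state the date from which the 3 years run.
3. In Trial Data Collection, say that control-site eligibility is judged by the chart-review form's rule.

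The cost is a few lines of protocol text and one revised template sent to the Sc sites. No new data are needed. The database already records which inclusion each man met, so the number of third-group men who were sent a note can be counted and reported.
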